Subjects prematurely discontinued from treatment, but wishing to continue in the study, will return for an ET Visit 8 weeks after the last dose of study drug. The post-treatment discontinuation follow-up for subjects wishing to continue in the study is detailed below:

- If the reason for study discontinuation is disease progression, the subjects will be contacted by telephone for information on survival, AEs, and concomitant medications every 8 weeks, for a total observation period of 52 weeks.
- If the reason for study discontinuation is different from disease progression, subjects will continue to attend scheduled tumour assessments (at which AE and concomitant medication information will also be collected) up to disease progression or Week 52, whichever occurs first. If these subjects subsequently experience disease progression then they will continue to be followed up by telephone every 8 weeks from that point of identification and for a total observation period of 52 weeks, as described for subjects discontinued from study drug due to disease progression.

Clinical assessments will be performed before the start of each treatment cycle by the Investigator. Tumour assessments for the purpose of assessing subject eligibility and medical care will be performed by the investigational site at Screening and Weeks 12, 28, and 52 (EOS/ET Visit).

The primary endpoint is BORR, defined as the proportion of subjects in each treatment group that achieve a best overall response of either CR, CRu or PR up to Month 7 (Week 28, i.e., 6 months after completion of rituximab induction) based on central radiology review in accordance with the response criteria for malignant lymphoma.¹³ An exploratory analysis using the Lugano criteria¹⁴ will also be performed as described in Section 3 and Section 9.4.1.3.

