The exact description of the treatment assigned to the individual subject then will be accessible. Emergency unblinding can thus be made for any subject without affecting the double-blind nature of the study. Subject treatment information may only be accessed in the event of an emergency and out of necessity to know the identity of the allocated study drug in order to institute appropriate therapeutic management. Should a situation arise where unblinding is urgently required (i.e. knowledge of treatment code is required to adequately manage a life-threatening situation), the Investigator at that study site may perform immediate unblinding through IWRS. If time allows, the Investigator may contact the Sponsor designee MM prior to unblinding the individual subject to discuss the rationale for emergency unblinding.

In the event that emergency unblinding is performed, the Investigator can view and must print the unblinded confirmation document from IWRS. The Investigator must record on the confirmation document printout the reason for the emergency unblinding and sign the document. The confirmation document must then be kept in a safe place until the end of the study. Once a randomisation code has been broken for a subject, he/she must be withdrawn from the study. The Investigator must inform the Sponsor designee MM in writing within 24 hours. An SAE form should be completed and reported in accordance with Section 8.4.2.

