7.2 Subject Discontinuation/Withdrawal from the Study

Subjects may withdraw from the study at any time at their own request, or they may be withdrawn at any time at the discretion of the Investigator or Sponsor/designee for safety, behavioural, or administrative reasons, or the inability of the subject to comply with the protocol required schedule of study visits or procedures at a given study site.

The decision to withdraw consent and discontinue participation in the study will not prejudice the subject's future medical treatment in any way. If a subject does not return for a scheduled visit or is lost to follow-up, every effort will be made to contact the subject. All attempts to contact the subject and information received during contact attempts must be documented in the subject's medical record. In any circumstance, every effort will be made to document subject outcome, if possible. The Investigator should inquire about the reason for withdrawal and request the subject to return for the EOS/ET (Week 52) Visit, if applicable, and follow-up with the subject regarding any unresolved AEs. The Investigator or sub-investigator will be responsible for reporting subject withdrawal to the Sponsor/designee. Subjects who withdraw after randomisation are not to be replaced and their randomisation number will not be re-used. If these subjects subsequently experience disease progression, then they will continue to be followed up as described in Section 4.1.1.

If a subject withdraws from the study, and also withdraws consent for disclosure of future information, no additional data should be collected. The Sponsor/designee may retain and continue to use any data collected before such withdrawal of consent.

Subjects shall be withdrawn during the course of the study when subject well-being is at risk, including but not limited to:

- Unacceptable AE.
- Subject is confirmed to be pregnant.

Subjects who experience disease progression in accordance with published response criteria for malignant lymphoma ¹³ (per Investigator assessment) are expected to be withdrawn from study drug, to attend the ET Visit, and to be followed up by telephone for survival as described in Section 4.1.1. Subjects who wish to remain in the study but withdraw from the study drug for any reason other than disease progression will return for an ET Visit and continue to attend scheduled tumour assessments up to disease progression or Week 52, whichever occurs first.

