9.3 Populations for Analyses

9.3.1 Intent to Treat Population

The Intent to Treat (ITT) Population will include all randomised subjects. The primary efficacy analysis will be based on the ITT Population.

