9.4.1 Efficacy Analyses

9.4.1.1 Analysis of Primary Efficacy Endpoint

The primary efficacy endpoint is the BORR i.e., the proportion of responders in each treatment arm who achieve a best overall response of either CR, CRu or PR up to Month 7 (Week 28) based on central radiology review in accordance with the response criteria for malignant lymphoma.¹³ Subjects who are included in the ITT Population but do not have efficacy assessments will be assessed as non-responders. The estimated difference (DRL_RI minus MabThera[®]) and its 95% CI will be obtained using the test -based exact binomial confidence interval method.^{27, 28} Equivalence will be concluded for FDA if the 90% CI and for EMA if the 95% CI of the BORR difference is completely contained within the pre-defined interval (-17%, 17%).

CCI . Full details

of the primary endpoint analysis including multiplicity considerations will be provided in the SAP.

Various sensitivity analyses will be conducted to confirm the robustness of the primary efficacy analysis result, including but not limited to:

• CCI

•	
	CCI
•	
	CCI
•	
	CCI

Additional details regarding sensitivity analyses for inter current events due to COVID-19 will be available in SAP.

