10.1.11 Protocol Deviations

All deviations from the approved protocol must be documented and notified to the Sponsor/CRO at the earliest. The Investigator should not deviate from the protocol, except for subject safety reasons, in which case the deviation must be reported to the Sponsor/CRO immediately. The Sponsor will not assume any resulting responsibility or liability from unapproved deviations. The Investigator, according to applicable regulations and the Ethics Committee's established procedures, will inform the Ethics Committee of protocol deviations.

All instances where the requirements of the study protocol are not complied with, will be captured in the eCRF and the study monitor will prepare a protocol deviation/violation log. Corresponding subjects may be withdrawn from the study at the discretion of the Sponsor/designee. Deviations from the study protocol should not be made other than as part of a protocol amendment. An amendment must be agreed upon by the Sponsor, but not implemented until written IEC/IRB approval is obtained, except where necessary to eliminate an immediate hazard to study subjects or when the change(s) involves only logistical or administrative aspects. Protocol deviations/violations and the reason why they occurred will be documented in the clinical study report.

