3.2 Definition of Endpoints / Variables

3.2.1 Definition of Efficacy Endpoints / Variables

3.2.1.1 Definition of the Primary Efficacy Endpoint / Variable

BOR up to Week 28 is defined as the best overall response at any radiologic tumor evaluations (based on central radiology review applying the Cheson 1999² response criteria for malignant lymphoma) up to the end of the allowed window for the Week 28 evaluations. Unscheduled and early termination evaluations will be only considered if they are complete and performed up to the end of the allowed window for the Week 28 evaluations.

[name] S.A	
Protocol RI-01-006	

The primary efficacy endpoint used in the statistical analysis is a binary (response / non-response) BOR up to Week 28 version is defined below. The impact of Intercurrent Events on binary BOR up to Week 28 is not described here but in Section 4.10.2.

For subjects with known tumor response at both Week 12 and Week 28, the definition of binary version of BOR up to Week 28 (the primary efficacy endpoint in the statistical analysis) is:

Response at Week 12	Response at Week 28	Binary version of BOR up to Week 28
CR, CRu or PR	Any known	Response
Any Known	CR, CRu or PR	Response
SD or PD	SD or PD	Non-Response

For subjects with a missing / unknown ("unknown" covers "not evaluable", "not available", "subject not anymore in the study", etc.) tumor response at Week 12 or at Week 28 and tumor response known at the other time-point, the definition of binary version of BOR up to Week 28 is:

Response at Week 12	Response at Week 28	Binary version of BOR up to Week 28
CR, CRu or PR	Missing / Unknown	Response
Missing / Unknown	CR, CRu or PR	Response
SD or PD	Missing / Unknown	Non-Response
Missing / Unknown	SD or PD	Non-Response

For subjects with only missing / unknown tumor responses, the definition of binary version of BOR up to Week 28 is:

Response at Week 12	Response at Week 28	Binary version of BOR up to Week 28
Missing / Unknown	Missing / Unknown	• Non-Response for main analysis using the exact score method, sensitivity analysis using stratified Mantel- Haenszel method, and FDA main estimand
		• Missing for sensitivity analyses within the estimand framework (except FDA main estimand) using multiple imputation approaches and for supplementary analyses as described in Section 4.10.2.3

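### A code break requires withdrawal from the study, and a deviation may lead to it; neither rule secures the later scans and survival contact kept for subjects who only stop study drug

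*Protocol*

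**What the plan says.** **Rules that end participation.** Protocol section 6.4.1, on emergency unblinding: "Once a randomisation code has been broken for a subject, he/she must be withdrawn from the study". Section 10.1.11, on protocol deviations: "Corresponding subjects may be withdrawn from the study at the discretion of the Sponsor/designee". Section 7.2 adds that "they may be withdrawn at any time at the discretion of the Investigator or Sponsor/designee for safety, behavioural, or administrative reasons". The first rule is mandatory and the other two are discretionary. Sections 6.4.1 and 10.1.11 are silent on scans and survival contact afterwards.

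**Rules that keep follow-up going.** Section 4.1.1 covers subjects who stop treatment without progression and wish to stay: "subjects will continue to attend scheduled tumour assessments", up to progression or Week 52. Sections 4.5, 7.2, 8.1.2 and 8.1.4 say the same. Section 4.5.3 defines the end of study as 52 weeks of follow-up for every enrolled subject except those lost or dead. Section 8.4.2 records adverse events to the later of the ET Visit or Week 52, with exceptions only for withdrawn consent or loss to follow-up. Section 7.2 also mentions follow-up of withdrawn subjects who later progress.

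**Analysis.** "The Intent to Treat (ITT) Population will include all randomised subjects" (Protocol 9.3.1). "Subjects who withdraw after randomisation are not to be replaced and their randomisation number will not be re-used" (7.2). "Subjects who are included in the ITT Population but do not have efficacy assessments will be assessed as non-responders" (9.4.1.1). SAP section 3.2.1.1 allows early-termination scans: "Unscheduled and early termination evaluations will be only considered if they are complete and performed up to the end of the allowed window" for Week 28.

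**The concern.** The protocol generally separates stopping study drug from leaving the study. The code-break rule does not, and the deviation rule need not. Applied literally, they end collection of outcomes that are already scheduled and that the ITT analysis wants.

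For code breaks the missing data may be informative, because section 6.4.1 reserves unblinding for emergencies and gives a life-threatening situation as its example. The rule is also not needed to protect the endpoint. The same section says that an emergency code break leaves the double-blind design intact, and response for the efficacy endpoints is assessed by the central imaging vendor (section 8.2), not by the investigator who has seen the code.

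At stake are the primary outcome of a subject who would have responded between Week 12 and Week 28, the Week 28 ORR and CR rates, and later DOR, PFS and OS information.

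**Working it through.** **Step 1. What becomes of a withdrawn subject** (SAP 3.2.1.1, main analysis):

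| State when the subject leaves | BOR up to Week 28 | Not secured |
|---|---|---|
| CR, CRu or PR already seen | Response, kept | Week 28 ORR and CR; later DOR, PFS, OS |
| SD at Week 12, no complete later scan in time | Non-response, although a response by Week 28 was possible | Primary outcome and all of the above |
| No Week 12 scan, complete ET scan in time | ET result counts | Week 28 ORR and CR; later DOR, PFS, OS |
| No usable scan | Non-response | Primary outcome and all of the above |
| Week 28 scan done | Unaffected | Later DOR, PFS, OS |

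Without later data, PFS is censored at the last tumour assessment (SAP Table 11) and OS at last contact (SAP 4.10.3.5).

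**Step 2. Can the ET scan stand in?** Where the protocol times the ET Visit, it is 8 weeks (56 days) after the last dose. A last dose on Day 1 gives Day 1 + 56 = Day 57. A last dose on Day 22 gives Day 22 + 56 = Day 78. Both lie in the SAP Week 12 window of Days 56 to 112 (Appendix 5). So an early withdrawal can still yield a valid Week 12 response, but not a Week 28 one. That timing is written for subjects who stop drug. None is given for a code-break withdrawal, and section 7.2 only has the investigator ask the subject to return.

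**Step 3. Size.** The plan's figure is 312 subjects, 156 per group. Its inputs (pooled rate, assumed difference, dropout) are redacted, so it cannot be uniquely reproduced. One set that matches is a rate of 0.75, no difference, one-sided alpha 0.025, 80% power and 12% dropout: 137 per group, 274/0.88 = 311.4, rounded up to 312. Only the 156 is used below.

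Assumptions, none from the documents unless stated: *k* = 1 to 8 such subjects per arm (8/156 = 5.1%), all without a usable scan; true rates 0.70 and 0.80; at the margin, 0.71 versus 0.88 (SAP 4.10.2.3.4). The method is two one-sided tests with an unpooled normal approximation, where the plan uses an exact interval:

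power = Φ((0.17 − |d|)/se − 1.96) + Φ((0.17 + |d|)/se − 1.96) − 1.

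- One would-be responder lost: 1/156 = 0.64 points in that arm.
- Loss in one arm only: bias = −p·k/156. For p = 0.80 and k = 5, −0.80 × 5/156 = −2.56 points.

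| k, one arm | Bias, p = 0.80 (points) | Power, 95% CI, p = 0.80 | Power, 95% CI, p = 0.70 |
|---|---|---|---|
| 0 | 0 | 92.7% | 81.2% |
| 1 | −0.51 | 92.2% | 80.8% |
| 3 | −1.54 | 90.1% | 79.0% |
| 5 | −2.56 | 86.5% | 76.1% |
| 8 | −4.10 | 78.0% | 69.5% |

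- Equal loss in both arms at the margin: apparent difference = 17 × (1 − k/156).

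| k per arm | Apparent difference (points) | One-sided error, 95% CI | One-sided error, 90% CI |
|---|---|---|---|
| 0 | 17.00 | 0.025 | 0.050 |
| 1 | 16.89 | 0.026 | 0.053 |
| 3 | 16.67 | 0.030 | 0.058 |
| 5 | 16.46 | 0.033 | 0.063 |
| 8 | 16.13 | 0.038 | 0.072 |

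Unbalanced loss costs power when the arms are truly equal. Balanced loss at the margin tilts slightly towards concluding equivalence. All rows are upper bounds, because any usable ET scan or Week 12 response restores the primary outcome.

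**The case against.** A reader might infer four stronger things. The documents do not support them.

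- **That ITT outcomes are thrown away.** They are not. ITT is all randomised subjects, earlier responses stand, and complete ET scans count up to the end of the Week 28 window.
- **That everyone withdrawn before Week 12 becomes a non-responder.** Only a subject with no usable scan by the end of the Week 28 window is set to non-response for lack of data. An ET scan 8 weeks after an induction dose falls in the Week 12 window.
- **That safety follow-up stops.** Section 8.4.2 makes no exception for code breaks, and section 8.4.8 follows SAEs to resolution or stabilisation.
- **That sponsor withdrawals for deviations are outcome-related.** Discretion alone does not show that. Section 10.1.11 names no outcome or arm trigger, and designated sponsor members are unblinded only after all subjects reach Week 28 and the database is locked (section 4.5.3).

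Two further objections carry weight. The protocol uses its terms loosely: section 4.1.1 speaks of study discontinuation while describing subjects who keep having scans, and section 7.2 asks for every effort to document outcome. A site might therefore continue follow-up anyway. That is a reason to settle the wording, not to rely on it. Missing-data analyses are also planned, including a tipping-point analysis. As described in SAP 4.10.2.3.1, however, that analysis varies only BOR values left missing by the derivation, and SD at Week 12 with nothing later is derived as non-response. The estimand tables are redacted, so their handling of such cases cannot be judged.

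**Conclusion.** The point holds as a small, inexpensive improvement that rests mainly on the mandatory code-break rule in section 6.4.1. That rule, and the discretionary one in section 10.1.11, do not fit the follow-up described in sections 4.1.1, 4.5, 4.5.3, 7.2 and 8.4.2. Followed as written, they leave later response, DOR, PFS and survival data unsecured in ITT subjects. For code breaks the loss may be informative.

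The size depends on a count that the documents do not give. One or two cases are negligible. The effect would matter only if such withdrawals were numerous or unbalanced, and nothing in the documents suggests that. The sample size and margin are not called into question.

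**What to change.** Reconcile sections 6.4.1, 7.2 and 10.1.11 with sections 4.1.1, 4.5, 4.5.3 and 8.4.2. State that a code break or a protocol deviation does not by itself end the already scheduled tumour assessments and survival follow-up, unless the subject withdraws consent. Keep the central readers blinded. Handle deviations through the per-protocol set, as Protocol 9.3.2 and SAP 4.4.2 already plan. A line in the SAP should say how these subjects are treated, since neither intercurrent-event table (SAP Tables 1 and 2) names unblinding or sponsor withdrawal.

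The cost is a wording amendment and continued scheduled visits for a few subjects whose investigator knows the treatment. No new procedure is needed. Whether study drug continues after a code break or deviation is a clinical matter and is not addressed here.

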6.5 Study Intervention Compliance

Study drug will be administered under the supervision of the Investigator and study site personnel.

At investigational site all activities related to handling of study drugs till administration to a subject should be performed by unblinded pharmacist/authorised designee/unblinded qualified physician. This person should be assigned by the Principal Investigator of a site and be responsible for:

- receipt of study drugs,
- storage of study drugs,
- dispensing of study drugs,
- preparation of study drugs for infusion,
- accountability and reconciliation of study drugs,
- preparation of study drugs for destruction (used, expired, not fit to use, unused after last subject last treatment).

Unblinded pharmacist/authorised designee/unblinded qualified physician will provide study drug to other investigators at a site after its dilution (as required by applicable instruction) ready for administration by means of infusion system.

Nobody except unblinded pharmacist/authorised designee/unblinded qualified physician among site's staff should be in contact with vials of study drugs – that keeps blinded design of the study.

Unblinded pharmacist/authorised designee/unblinded qualified physician may not be in direct contact (may not treat/administer study drug) subjects enrolled in the study.

It is expected that at each investigational site there should be 2 unblinded pharmacist/authorised designee/unblinded qualified physician – to ensure appropriate handling of study drugs while absence of one of the unblinded person (e.g., due to vacation).

Compliance will be monitored by study personnel at the study site by using the source documents and the eCRFs. The unblinded pharmacist/authorised designee/unblinded qualified physician responsible for drug preparation will keep accurate and complete dispensing and accountability forms showing the receipt and dispensation of the study drug.

6.6 Study Treatment Accountability

Records will be maintained of the delivery of study drugs to the study centres, the inventory at the study centres, the use of each subject and the return to the Sponsor/designee.

These records shall include dates, quantities, batch numbers, expiry dates, and the unique code numbers assigned to the study medication and to the study subjects.

The Investigator shall be responsible for ensuring that the records adequately document that the subjects were provided the study drug specified by the IWRS and that all study medication received from the Sponsor/designee is reconciled.

6.7 Concomitant Therapy

Medications that are considered necessary for the subject's safety and well-being may be given during the course of the study at the discretion of the Investigator and must be recorded in the appropriate sections of the eCRF.

All medications taken by a subject within 1 month prior to screening are regarded as **prior medication** and must be documented as such in the eCRF.

All medications still being taken by a subject at the time of signing the Informed Consent Form (ICF) and which continue to be taken during the study, as well as all medications started after signing of the ICF, are regarded as **concomitant medication** and must be documented as such in the eCRF. The use of concomitant therapy, including prescription and non-prescription drugs, non-drug therapy, and dietary supplements and herbal preparations, is permitted as appropriate to treat AE or co-morbid conditions. Concomitant administration of any other experimental drug or a concomitant chemotherapy, anticancer hormonal therapy, radiotherapy, or immunotherapy is prohibited during study participation. This includes administration of rituximab not included in the protocol-defined treatment. If a subject requires tumour targeting treatment for FL other than the protocol-defined treatment with rituximab monotherapy, including, but not restricted to, other immunotherapies, chemotherapy, and radiotherapy, this will be defined as disease progression. The date the concomitant treatment was initiated will be collected in the eCRF.

Any other medication or vaccine (including over-the-counter or prescription medicines, vitamins, and/or herbal supplements) that the subject is receiving at the time of enrolment or receives during the study must be recorded along with:

- reason for use
- dates of administration including start and end dates
- dosage information including dose and frequency

The MM should be contacted if there are any questions regarding concomitant or prior therapy.

During their participation in the study, subjects should not take any prescription or non-prescription drug without the permission of the Study Investigator. However, the permission of the Study Investigator should be waived for medical emergencies.

